8 CORRELATIVE STUDIES

8.1 Correlative Studies: Circulating Biomarkers

Based on findings from preliminary studies, we propose here to evaluate the changes in blood circulating SDF1 α and circulating myeloid cells throughout the treatment course to explore potential associations between the changes in these biomarkers and resistance to treatment. In exploratory studies, we will evaluate several other cytokines using multiplex protein array (Meso-Scale Discovery, Inc.).

8.1 Experimental Design

Blood will be drawn by venipuncture, and the first 7-10 ml blood will be excluded or used for other analysis. The following 8 ml will be collected in an EDTA tube. The EDTA tube with the blood sample will be shipped in wet ice within 2 hours of drawing for further processing at Steele Laboratory at MGH. We will analyze the correlation between plasma SDF1 α and circulating myeloid cells with multiple measures of outcome (ORR, TTP, OS) in patients with borderline resectable pancreatic cancer before, during, and after treatment.

8.2 Collection

To this end we will measure circulating biomarkers at the following stages:

- (i) Pretreatment
- (ii) At beginning and end of FOLFIRINOX therapy
- (iii) After radiation therapy
- (iv) One month post-operatively
- (v) At the time of disease progression

Samples will be collected at the following timepoints:

- a. Prior to the start of therapy
- b. Day 8 of Cycle 1 of FOLFIRINOX
- c. After Cycle 4 (and Cycle 8 if received) of FOLFIRINOX
- d. After chemoradiation OR pre-operatively
- e. 1 month after completion of therapy.
- f. 1 month after pancreaticoduodenectomy (Whipple procedure)

g. Within 2 weeks after radiologic progression

8.3 Shipping Instructions

The tube containing the blood should be shipped with the following information

1. Study Number at the DF/HCC
2. Patient number on the study
3. Patient's initials
4. Treating physician's name
5. Date of collection
6. Date of shipping

The tube of blood should be placed in a sealable container and placed in a box with the necessary information. The box should be marked Biohazard.

The blood will be shipped to:

[REDACTED]

8.2 Patient Reported Outcomes

QOL (EORTC QLQ-C30, version 3.0), symptoms (ESAS-r), and mood (HADS) will be assessed at time of informed consent prior to neoadjuvant therapy; at weeks 3, 7, 11, and 15 of neoadjuvant chemotherapy; at week 2 of capecitabine chemoradiotherapy; and during active follow up. All PRO administrations have a window of +/- 2 weeks from the assigned assessment timepoint.

Pretreatment	FOLFIRINOX	ChemoRT	Post-op
At time of informed consent	Day 1 of cycles 2,4,6,8 [Week 3, 7, 11, 15]	Week 2, day1	At 3 month follow up, then every 6months for the first 2 years of follow up, then yearly until completion of year 5
EORTC QLQ-C30	EORTC QLQ-C30	EORTC QLQ-C30	EORTC QLQ-C30
ESAS-r	ESAS-r	ESAS-r	ESAS-r
HADS	HADS	HADS	HADS

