5.2 Agent Administration

Study participants will receive up to 8 cycles of FOLFIRINOX as indicated in the study schema. All treatments shall be administered according to institutional standard of care.

5.2.1 5-Fluorouracil: 5-FU will be administered at a dose of 400 mg/m² push per institutional standard on day one, followed by a 1200 mg/M²/d by continuous

infusion via an ambulatory infusion pump for the subsequent two days. 5-Fluorouracil is not a vesicant or irritant. Initial dose of 5-FU may be reduced if necessary; then gradually increased to full dose if tolerated. All dose adjustments are to be made at the discretion of the treating medical oncologist.

5.2.2 Oxaliplatin: Oxaliplatin will be administered as a dose of 85 mg/m² by intravenous infusion over 120 minutes. Infusion time may be prolonged (up to 6 hours) in patients experiencing pharyngolaryngeal dysesthesia. Oxaliplatin is unstable in the presence of chloride or alkaline solutions. Do NOT mix or administer oxaliplatin with saline or other chloride-containing solutions. Do NOT administer other drugs or solutions in the same infusion line. Flush IV lines/catheters with Dextrose 5% in Water both before and after oxaliplatin administration. Initial dose of Oxaliplatin may be reduced if necessary; then gradually increased to full dose if tolerated. All dose adjustments are to be made at the discretion of the treating medical oncologist.

5.2.3 Leucovorin: Leucovorin (400 mg/m²) will be diluted with 5% dextrose and administered concurrently (in separate containers using a Y-type administration set) by IV infusion over 2 hours.

5.2.4 Irinotecan: In this study irinotecan will be administered as a dose of 180 mg/m² by intravenous infusion over 90 minutes. Initial dose of Irinotecan may be reduced if necessary; then gradually increased to full dose if tolerated. All dose adjustments are to be made at the discretion of the treating medical oncologist.

5.2.5 Capecitabine: The dose of capecitabine will be given orally 825 mg/m² BID (total 1650 mg/m² per day) for a total of 10 days M-F during the week of, and the week after, proton beam radiation; or the two weeks of photon radiation. The dose of capecitabine will be fixed unless there are dose level reductions. The daily dose will be administered in two divided doses approximately 12 hours apart. The medication should be given

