5.2.6 Radiation Therapy

5.2.6.1 Simulation and Planning

Tumor volume will be defined on the basis of CT and MRI imaging findings and operative notes and findings. The primary tumor and any clinically enlarged lymph nodes will be treated with a margin of 2 cm to include peripancreatic nodes. The porta hepatis, celiac axis, superior mesenteric artery (SMA) root, and the pancreaticoduodenal nodes will also be treated.

Total dose will be prescribed to the 95 to 100% isodose line based on coverage and will be 25 CGE protons in 5 fractions (5 Gy/day) or 30 Gy photons in 10 fractions (3 Gy/day) with multifield techniques. A dose painted boost to involved vasculature is permitted to a total dose of 30 Gy. Radiation treatment assignment will be based on resource availability at the time of radiation planning.

Patients will be simulated supine. Intravenous and oral contrast will be administered per standard department protocol. 4-D planning CT will be obtained for treatment planning to ascertain the extent of tumor motion.

The Gross Tumor Volume (GTV) is defined as the gross primary tumor and any lymph nodes enlarged over 1 cm during simulation using contrast given during CT or MRI. The clinical target volume (CTV) will also include the following at-risk nodal basins: porta hepatis, celiac axis, superior mesenteric artery, and pancreaticoduodenal nodes as defined by the inner-third of the duodenum. Planning target volume (PTV): PTV will be customized based on 4D CT scan. Generally 0.5 cm expansion will be used, except for superiorly/inferiorly 0.7 cm will be used.

Computerized dosimetry is required if more than two fields are used. All fields must be simulated using a machine that duplicates the geometry of the actual treatment machine. Patient contours and isodose plots are required. Isodose plots must account for the effect of all treated fields, including any blocking used.

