5.2.6.2 Treatment

All radiation treatment will be given with the patient at the Francis H. Burr Proton Therapy Center or the Clark Center for Radiation Oncology at MGH. Film or digital images will be taken prior to each treatment in accordance with the Department of Radiation Oncology’s standard practice for all patients. These images are used to verify the position of the patient and the aperture. These digital images are permanently stored electronically for each patient.

Radiation treatment must start on a Monday-Wednesday. If the proton center is unexpectedly not functioning for 1-2 days, these fractions may be made up the following week. However, if the proton center is not functioning longer than 2 days, patients may receive photon radiation for the remaining fractions. If radiation therapy start is delayed beyond 4 weeks after completion of FOLFIRINOX due to toxicity, the patient will proceed to radiation therapy on study at the discretion of the treating investigator.

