5.2.7 Other Modalities and Procedures

5.2.7.1 Surgery: Surgery will be performed one to four weeks after completion of capecitabine therapy. If surgery is delayed beyond four weeks after completion of capecitabine, the patient will be taken off study. At laparotomy, the liver and pancreas will be examined by palpation and inspection. In the absence of metastases, tumor mobilization and surgical resection will be performed. A pancreaticoduodenectomy (Whipple procedure) or distal pancreatectomy with standard lymphadenectomy will be done. This involves dissection up to the superior mesenteric artery, with skeletonization of the right lateral and anterior aspects of the vessels. Feeding jejunostomy and gastrostomy tubes may be placed at the discretion of the operating surgeon.

5.2.7.2 Pathology: Processing the specimen and pathology will be reported according to the AJCC Cancer Staging Manual, 6th Edition. Pancreatic transection margin, and the bile duct margin will be evaluated on frozen section. Recorded on permanent section will be: tumor size, degree of differentiation (well, moderate, poor), lymph node status, and margin status.

5.2.7.3 Chemotherapy: Patients may receive adjuvant chemotherapy after at the discretion of the treating investigator. If adjuvant chemotherapy is administered, at minimum, administration of FOLFIRINOX therapy will be contingent on patients meeting original inclusion criteria (lab parameters and performance status). Physicians may opt to provide FOLFOX or FOLFIRI in the postoperative setting, with the full FOLFIRINOX regimen administered only when the patient is able to tolerate this therapy. If there is evidence of progression, patients will be withdrawn

from the study and as per NCCN guidelines, proceed to second-line therapy (likely gemcitabine-based chemotherapy.) Appropriate dose reductions and modifications can be made at the discretion of the treating physician.

5.3 General Concomitant Medication and Supportive Care Guidelines:

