6.3 Capecitabine and Radiation

Hematologic and Non-Hematologic Toxicity

Capecitabine will be held for any Grade 3 or 4 toxicity. After toxicity resolves to \leq grade 1, capecitabine will be resumed at 600 mg/m² BID to complete the 10 weekdays of therapy.

Capecitabine can be held a maximum of 7 days. If further grade 3 or 4 toxicity is noted at the reduced dose level, after toxicity resolves to \leq grade 1, capecitabine will be resumed at 500 mg/m² BID to complete two weeks of therapy. If the second dose reduction is not tolerated, capecitabine will be stopped. Patients will keep a capecitabine diary and will record the number of capecitabine tablets and the time that they take the tablets.

Grade 3 or 4 toxicities that are due to biliary ductal dilatation and resolved with placement of a biliary stent or with biliary stent change will not require a dose reduction of capecitabine or radiation therapy after stent placement. Therapy may be withheld for procedures like ERCP and biliary stenting, and restarted at the treating physician's discretion.

Radiation therapy will be held for Grade 3 or 4 nausea that is not well controlled with anti-emetic support, until nausea resolves to Grade 2 or less. It will then be resumed at same dose.

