9 STUDY CALENDAR

Baseline laboratory evaluations are to be conducted within seven days prior to study entry. Non-laboratory evaluations (imaging, etc) must be done ≤ 42 days (6 weeks) prior to the start of therapy.

All pre-study assessments must be performed prior to administration of any study medication, unless otherwise noted. All study assessments and medications should be administered within ± 3 days of the protocol-specified date, unless otherwise noted. All follow up assessments may be performed ± 21 days of the protocol-specified date.

Required Data Table

Tests and Observation	Prior to Study	Day 1 of each cycle of FOLFIRINOX and at Restaging	During ChemoRT	Post-op F/U(2)
Signed informed consent and registration	X			

History	X			
Physical Examination	X	X	X weekly	X
Vital Signs and performance status	X		X weekly	X
Height/Weight/Surface Area	X		X at start of ChemoRT	
Toxicity Assessment		X	X weekly	X
Laboratory (1):				
CBC/plts/diff	X	X	X Days 1, 8 and 15	X
Serum chemistries (Na, K, BUN, Cr, Glucose, Calcium, Albumin, AST, ALT, Total bilirubin, Alkaline phosphatase)	X	X	X Days 1, 8 and 15	X
Creatinine clearance calculation (Cockcroft Gault)	X	X (day 1 of cycles 1, 3, 5, and 7 only)	X Days 1, 8 and 15	
CA19-9	X	X (at restaging visits only)	X, Days 1 and 15	X
CEA	X	X (at restaging visits only)	X Days 1 and 15	X
Pregnancy test*	X			
Staging:				

Chest CT Abd-pelvic CT (or MRI)	X	X after first week of cycle 4 and first week of last cycle of FOLFIRINOX		X
Tumor SNaPshot (3)	X			X
Nutritional Assessment	X(4)	X(4)	X(4)	
Correlative Studies	X(5)	X(5)	X(5)	X(5)
PROs (EORTC QLQ, ESAS-r, HADS) (details in section 8.2)	X	X	X	X

Notes

- (1) Pre-study Laboratory values need to be obtained within 7 days of study entry.
- (2) Post-op follow up schedule is as follows. For years 1 and 2 follow up will be visit and labs at least every three months, scans at least every 6 months, For year 3, visit and labs will be at least every 3 months and scans will be at least every 12 months. For years 4 and 5 visit and labs will be at least every 6 months and scans will be at least every 12 months. For patients with R0, R1 and R2 resections, the first post-op CT scan, visit and labs are 3-8 weeks postoperatively. All follow up assessments may be performed +/-21 days of the protocol-specified date.
- (3) Tumor SHaPshot will be done once for each participant, either on the pre-treatment biopsy specimen (if available) or on the resected tumor specimen.

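### The two-week PRO window lets the only chemoradiation questionnaire be completed before the first fraction or after the course has ended

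*Combined protocol and SAP*

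**What the plan says.** Section 8.2 (Patient Reported Outcomes) schedules the QLQ-C30, ESAS-r and HADS at consent, four times during FOLFIRINOX, once during chemoradiation, and then in follow-up. The chemoradiation set is due "at week 2 of capecitabine chemoradiotherapy"; the table in that section puts it on day 1 of that week. One timing rule covers every set: "All PRO administrations have a window of +/- 2 weeks from the assigned assessment timepoint".

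Section 9 has a tighter default, "All study assessments and medications should be administered within" three days of the planned date, but it gives way where another section says otherwise. The calendar's PRO row marks the During ChemoRT column and refers to section 8.2 for details.

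The length of the course follows from four other places:

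- Section 5.2.5 gives capecitabine for "a total of 10 days M-F during the week of, and the week after, proton beam radiation", or over the two weeks of photon treatment.
- Section 5.2.6.1 sets five proton or ten photon fractions.
- Section 5.2.6.2 adds: "Radiation treatment must start on a Monday-Wednesday".
- Section 5.2.7.1 says: "Surgery will be performed one to four weeks after completion of capecitabine therapy".

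Section 14.4 summarises the PROs descriptively for the whole cohort. It has no rule for assigning a form to a treatment period by the date it was completed.

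**The concern.** Each half of the window is 14 days, longer than the 12-day course it is meant to sample. Nothing in section 8.2 ties the form to the first fraction, the last capecitabine dose or surgery.

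This is the only PRO set linked to chemoradiation, and the instruments look back only a short way. HADS and most QLQ-C30 items ask about the past week. ESAS-r asks about the present on the form, or the previous 24 hours in the background section. A set completed before day 1 therefore carries no chemoradiation exposure, yet it meets the stated rule and would be summarised as the chemoradiation score. At stake is whether the trial can describe quality of life, symptoms and mood during chemoradiation under objective 1.3.9.

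**Working it through.** This is calendar arithmetic.

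**Day convention.** Section 6.2.1 gives 14-day cycles, so day 1 of cycle c is day 14(c - 1) + 1. Cycles 2, 4, 6 and 8 start on days 15, 43, 71 and 99, which are the first days of weeks 3, 7, 11 and 15. This reproduces the weeks printed in section 8.2 and fixes the rule that week n day 1 is day 7(n - 1) + 1. Chemoradiation week 2 day 1 is therefore 7 × 1 + 1 = day 8.

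**Window.** 8 - 14 = day -6; 8 + 14 = day 22. Inclusive length: 22 - (-6) + 1 = 29 days.

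**Monday start.** I assume capecitabine begins with the first fraction and runs for ten consecutive weekdays.

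- Capecitabine: days 1-5 and 8-12, so the last dose is on day 12. Ten photon fractions also end on day 12; five proton fractions end on day 5.
- Earliest surgery: 12 + 7 = day 19.
- Window days before the first fraction: -6 to 0, which is 7.
- Window days within the course: 1 to 12, which is 12.
- Window days after the last capecitabine dose: 13 to 22, which is 10.
- Of those 10, days strictly after the earliest surgery: 20 to 22, which is 3.
- Check: 7 + 12 + 10 = 29.

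**Sensitivity.** With a Tuesday or Wednesday start, the tenth weekday is day 14 and the earliest surgery is 14 + 7 = day 21. Week 2 day 1 can then mean day 8, or the calendar Monday of the second week (day 7 or day 6).

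| Start and reading | Window | Days before first fraction | Days after last capecitabine | Days after earliest surgery |
|---|---|---|---|---|
| Monday | -6 to 22 | 7 | 10 | 3 |
| Tuesday or Wednesday, day 8 | -6 to 22 | 7 | 8 | 1 |
| Tuesday, calendar Monday (day 7) | -7 to 21 | 8 | 7 | 0 |
| Wednesday, calendar Monday (day 6) | -8 to 20 | 9 | 6 | 0 |

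Section 6.3 also allows a delay: "Capecitabine can be held a maximum of 7 days". With a Monday start and a full hold, the last dose moves to 12 + 7 = day 19 and the earliest surgery to 19 + 7 = day 26. That is beyond day 22, so no post-operative day remains in the window.

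**Neighbouring windows.** The cycle 2 window is 15 ± 14 = days 1 to 29 and the cycle 4 window is 43 ± 14 = days 29 to 57. They share one boundary day, and the first opens on cycle 1 day 1. If chemoradiation began straight after cycle 8 (an assumption, on day 99 + 14 = 113), its day 8 would be day 120 and its window would open on day 120 - 14 = 106. The cycle 8 window, 99 ± 14, closes on day 113, so one form could fit both timepoints.

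**The case against.** The best counter-argument is intent. The calendar column and the wording of section 8.2 both place the form in chemoradiation. Section 9 provides weekly examinations and toxicity checks, with blood tests on days 1, 8 and 15, so a contact already falls on the assigned day and most forms may well be completed then. This makes gross mistiming less likely, but it does not change the rule: the explicit window displaces the three-day default and is not limited to the phase.

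A reader might infer more than the documents support, in four ways:

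- **That post-surgical scores are a substantial problem.** They need surgery in the first days of a one-to-four-week range with no capecitabine hold. The overlap is 3 days at most and disappears in several variants.
- **That only 12 of 29 forms in the window, 41%, would be valid.** That figure is a share of calendar days. Nothing in the plan suggests completion is spread evenly. Forms completed soon after the last dose also still recall treatment days on the past-week items, up to day 18 for a Monday start, though not on ESAS-r.
- **That sections 8.2 and 9 contradict each other.** They do not; section 9 allows exceptions and refers to section 8.2.
- **That a planned treatment effect is biased.** Section 14.4 plans only description of the whole cohort, with no chemoradiation contrast.

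The objection to a blanket three-day window also stands. Chemotherapy cycles may be shifted or held, and in a trial of 50 patients a strict window could lose forms.

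**Conclusion.** The concern holds for the chemoradiation questionnaire. As written, the rule accepts a form completed up to 7 days before the first fraction (8 or 9 under the calendar-Monday reading of a Tuesday or Wednesday start) or up to 10 days after the last capecitabine dose. The exposure before radiation is present in every variant tried; the post-operative overlap is marginal. These figures assume that capecitabine starts with the first fraction and runs without interruption, apart from the hold variant.

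The documents do not show how many forms would be mistimed, so this is a defect in the rule and not an estimate of misclassification. It affects the descriptive objective 1.3.9 only. The R0 endpoint and its decision rule are not involved. It should be corrected, because it concerns the only PRO set tied to chemoradiation and the correction is cheap.

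**What to change.** **Section 8.2 (Patient Reported Outcomes).** State that the chemoradiation set is completed on or after the first fraction and before surgery, preferably at the existing day-8 contact and by the end of capecitabine. Leave the two-week window in place for the other timepoints.

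**Section 14.4.** Add that each PRO form is assigned to a treatment period by its actual completion date relative to the first FOLFIRINOX dose, the first fraction, the last capecitabine dose and surgery. Forms completed before the first fraction are then not summarised as chemoradiation scores, and a form that fits two windows has one defined place.

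**Cost.** Two short wording changes. The instruments already carry a date field, so the assignment rule also works for forms already collected, and no new visit is needed. A few chemoradiation forms may be reclassified or counted as missing; the report should give that number.

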8.3 Correlative Studies: SNaPshot analysis

Mutational analysis will be performed by tumor SNaPSHOT for the mutations listed in section 2.2.6.1. Paraffin-embedded block or ten unstained slides will be used from the untreated biopsy specimen obtained at the time of upper endoscopy or initial diagnostic biopsy. Analysis will be performed as described by Dias-Santagata (47) at the Translational Research Laboratory at MGH.

9 STUDY CALENDAR

Baseline laboratory evaluations are to be conducted within seven days prior to study entry. Non-laboratory evaluations (imaging, etc) must be done ≤ 42 days (6 weeks) prior to the start of therapy.

All pre-study assessments must be performed prior to administration of any study medication, unless otherwise noted. All study assessments and medications should be administered within ± 3 days of the protocol-specified date, unless otherwise noted. All follow up assessments may be performed ± 21 days of the protocol-specified date.

Required Data Table

Tests and Observation	Prior to Study	Day 1 of each cycle of FOLFIRINOX and at Restaging	During ChemoRT	Post-op F/U(2)
Signed informed consent and registration	X			

History	X			
Physical Examination	X	X	X weekly	X
Vital Signs and performance status	X		X weekly	X
Height/Weight/Surface Area	X		X at start of ChemoRT	
Toxicity Assessment		X	X weekly	X
Laboratory (1):				
CBC/plts/diff	X	X	X Days 1, 8 and 15	X
Serum chemistries (Na, K, BUN, Cr, Glucose, Calcium, Albumin, AST, ALT, Total bilirubin, Alkaline phosphatase)	X	X	X Days 1, 8 and 15	X
Creatinine clearance calculation (Cockcroft Gault)	X	X (day 1 of cycles 1, 3, 5, and 7 only)	X Days 1, 8 and 15	
CA19-9	X	X (at restaging visits only)	X, Days 1 and 15	X
CEA	X	X (at restaging visits only)	X Days 1 and 15	X
Pregnancy test*	X			
Staging:				

Chest CT Abd-pelvic CT (or MRI)	X	X after first week of cycle 4 and first week of last cycle of FOLFIRINOX		X
Tumor SNaPshot (3)	X			X
Nutritional Assessment	X(4)	X(4)	X(4)	
Correlative Studies	X(5)	X(5)	X(5)	X(5)
PROs (EORTC QLQ, ESAS-r, HADS) (details in section 8.2)	X	X	X	X

Notes

- (1) Pre-study Laboratory values need to be obtained within 7 days of study entry.
- (2) Post-op follow up schedule is as follows. For years 1 and 2 follow up will be visit and labs at least every three months, scans at least every 6 months, For year 3, visit and labs will be at least every 3 months and scans will be at least every 12 months. For years 4 and 5 visit and labs will be at least every 6 months and scans will be at least every 12 months. For patients with R0, R1 and R2 resections, the first post-op CT scan, visit and labs are 3-8 weeks postoperatively. All follow up assessments may be performed +/-21 days of the protocol-specified date.
- (3) Tumor SHaPshot will be done once for each participant, either on the pre-treatment biopsy specimen (if available) or on the resected tumor specimen.
- (4) Nutritional assessment will include meeting with an oncology nutritionist for evaluation and education at the beginning of treatment. The patient will then track dietary protein intake throughout treatment until time of surgery. The patient's logged protein intake will be reviewed in post-op follow up by the treatment team. Both the nutritionist evaluation and protein tracking are optional resources available to patients and are not required by the protocol.
- (5) Peripheral blood for correlative studies will be obtained with clinical labs at pretreatment, day 8 of Cycle 1 FOLFIRINOX, at restaging visits, after proton beam radiation therapy/pre-operatively, 1 month after completion of therapy, 1 month post-operatively, and within two weeks of radiographic progression (these blood draws are optional).

